7. ADVERSE EVENTS: LIST AND REPORTING REQUIREMENTS

Adverse event (AE) monitoring and reporting is a routine part of every clinical trial. The following list of AEs (Section 7.1) and the characteristics of an observed AE (Section 7.2) will determine whether the event requires expedited reporting (via CTEP-AERS) **in addition to** routine reporting.

7.1 Comprehensive Adverse Events and Potential Risks List (CAEPR)

The Comprehensive Adverse Event and Potential Risks list (CAEPR) provides a single list of reported and/or potential adverse events (AE) associated with an agent using a uniform presentation of events by body system. In addition to the comprehensive list, a subset of AEs, the Specific Protocol Exceptions to Expedited Reporting (SPEER), appears in a separate column and is identified with ***bold*** and *italicized* text. The SPEER is a list of events that are protocol-specific exceptions to expedited reporting to NCI via CTEP-AERS (except as noted below). Refer to the 'CTEP, NCI Guidelines: Adverse Event Reporting Requirements'
http://ctep.cancer.gov/protocolDevelopment/adverse_effects.htm for further clarification.

The CAEPR may not provide frequency data; if not, refer to the Investigator's Brochure for this information.

NOTE: The highest grade currently reported is noted in parentheses next to the AE in the SPEER. Report **ONLY** AEs higher than this grade expeditiously via CTEP-AERS. If this CAEPR is part of a combination protocol using multiple investigational agents and has an AE listed on different SPEERs, use the lower of the grades to determine if expedited reporting is required.

7.1.1 CAEPR for MLN0128 (TAK-228)

Comprehensive Adverse Events and Potential Risks list (CAEPR) for MLN0128 (TAK-228) (INK128, NSC 768435)

The Comprehensive Adverse Events and Potential Risks list (CAEPR) provides a single list of reported and/or potential adverse events (AE) associated with an agent using a uniform presentation of events by body system. In addition to the comprehensive list, a subset, the Specific Protocol Exceptions to Expedited Reporting (SPEER), appears in a separate column and is identified with bold and italicized text. This subset of AEs (SPEER) is a list of events that are protocol specific exceptions to expedited reporting to NCI (except as noted below). Refer to the 'CTEP, NCI Guidelines: Adverse Event Reporting Requirements'
http://ctep.cancer.gov/protocolDevelopment/electronic_applications/docs/aeguidelines.pdf for further clarification. *Frequency is provided based on 252 patients.* Below is the CAEPR for MLN0128 (TAK-228)(INK128).

NOTE: Report AEs on the SPEER **ONLY IF** they exceed the grade noted in parentheses next to the AE in the SPEER. If this CAEPR is part of a combination protocol using multiple investigational agents and has an AE listed on different SPEERs, use the lower of the grades to determine if expedited reporting is required.

Version 2.2, April 26, 2016

Adverse Events with Possible Relationship to MLN0128 (TAK228) (CTCAE 4.0 Term) [n= 311]			Specific Protocol Exceptions to Expedited Reporting (SPEER)
Likely (>20%)	Less Likely (<=20%)	Rare but Serious (<3%)	
BLOOD AND LYMPHATIC SYSTEM DISORDERS			
	Anemia		Anemia (Gr 2)
CARDIAC DISORDERS			
		Cardiac arrest	
		Ventricular fibrillation	
GASTROINTESTINAL DISORDERS			
	Abdominal pain		Abdominal pain (Gr 2)
	Constipation		Constipation (Gr 2)
Diarrhea			Diarrhea (Gr 2)
	Dry mouth		Dry mouth (Gr 2)
Mucositis oral			Mucositis oral (Gr 2)
Nausea			Nausea (Gr 2)
Vomiting			Vomiting (Gr 2)
GENERAL DISORDERS AND ADMINISTRATION SITE CONDITIONS			
	Edema limbs		
Fatigue			Fatigue (Gr 2)
	Fever		Fever (Gr 2)
	General disorders and administration site conditions - Other (mucosal inflammation)		General disorders and administration site conditions - Other (mucosal inflammation) (Gr 2)
INFECTIONS AND INFESTATIONS			
	Urinary tract infection		Urinary tract infection (Gr 2)
INVESTIGATIONS			
	Creatinine increased		Creatinine increased (Gr 2)
		Electrocardiogram QT corrected interval prolonged	
	Platelet count decreased		Platelet count decreased (Gr 2)
	Weight loss		Weight loss (Gr 2)
METABOLISM AND NUTRITION DISORDERS			

Anorexia			Anorexia (Gr 2)
	Dehydration		Dehydration (Gr 2)
Hyperglycemia			Hyperglycemia (Gr 2)
	Hypokalemia		Hypokalemia (Gr 2)
	Hypomagnesemia		Hypomagnesemia (Gr 2)
	Hypophosphatemia		Hypophosphatemia (Gr 2)
MUSCULOSKELETAL AND CONNECTIVE TISSUE DISORDERS			
	Arthralgia		
	Back pain		Back pain (Gr 2)
	Pain in extremity		
NERVOUS SYSTEM DISORDERS			
	Dizziness		Dizziness (Gr 2)
	Dysgeusia		Dysgeusia (Gr 2)
	Headache		Headache (Gr 2)
PSYCHIATRIC DISORDERS			
	Insomnia		
RESPIRATORY, THORACIC AND MEDIASTINAL DISORDERS			
	Cough		Cough (Gr 2)
	Dyspnea		Dyspnea (Gr 2)
		Pneumonitis	
	Respiratory, thoracic and mediastinal disorders - Other (oropharyngeal pain)		
SKIN AND SUBCUTANEOUS TISSUE DISORDERS			
Pruritus			Pruritus (Gr 2)
Rash maculo-papular			Rash maculo-papular (Gr 2)

¹This table will be updated as the toxicity profile of the agent is revised. Updates will be distributed to all Principal Investigators at the time of revision. The current version can be obtained by contacting [contact]. Your name, the name of the investigator, the protocol and the agent should be included in the e-mail.

Adverse events reported on MLN0128 (TAK228) trials, but for which there is insufficient evidence to suggest that there was a reasonable possibility that MLN0128 (TAK228) caused the adverse event:

Cardiac disorders - Heart failure; Pericardial effusion; Sinus tachycardia

Eye disorders - Blurred vision; Eye disorders - Other (visual acuity reduced); Eye pain; Photophobia

Gastrointestinal disorders - Dyspepsia; Dysphagia; Esophagitis; Gastroesophageal reflux disease; Gastrointestinal disorders - Other (intestinal obstruction); Oral pain; Pancreatitis; Small intestinal obstruction; Small intestinal perforation; Toothache

General disorders and administration site conditions - Chills; Gait disturbance; Non-cardiac chest pain; Pain

Hepatobiliary disorders - Gallbladder obstruction

IMMUNE SYSTEM DISORDERS - Allergic reaction

Infections and infestations - Kidney infection; Lung infection; Sepsis; Skin infection; Upper respiratory infection

Injury, poisoning and procedural complications - Fall; Tracheal obstruction

Investigations - Alanine aminotransferase increased; Aspartate aminotransferase increased; Blood bilirubin increased; Cholesterol high; Lymphocyte count decreased; Neutrophil count decreased; White blood cell decreased

Metabolism and nutrition disorders - Hypercalcemia; Hypertriglyceridemia; Hypoalbuminemia; Hypocalcemia; Hyponatremia; Metabolism and nutrition disorders - Other (vitamin D deficiency)

Musculoskeletal and connective tissue disorders - Flank pain; Generalized muscle weakness; Musculoskeletal and connective tissue disorder - Other (muscle spasms); Myalgia

Neoplasms benign, malignant and unspecified (incl cysts and polyps) - Treatment related secondary malignancy

Nervous system disorders - Intracranial hemorrhage; Nervous system disorders - Other (carotid artery occlusion); Tremor

Psychiatric disorders - Anxiety; Confusion; Depression; Personality change

Renal and urinary disorders - Acute kidney injury; Hematuria; Urinary tract pain

Respiratory, thoracic and mediastinal disorders - Bronchopulmonary hemorrhage; Epistaxis; Hypoxia; Nasal congestion; Pleural effusion; Pneumothorax; Postnasal drip; Productive cough

Skin and subcutaneous tissue disorders - Dry skin; Hyperhidrosis; Rash acneiform; Urticaria

Vascular disorders - Flushing; Hypotension; Thromboembolic event

Note: MLN0128 (TAK228) in combination with other agents could cause an exacerbation of any adverse event currently known to be caused by the other agent, or the combination may result in events never previously associated with either agent.

7.2 Adverse Event Characteristics

- **CTCAE term (AE description) and grade:** The descriptions and grading scales found in the revised NCI Common Terminology Criteria for Adverse Events (CTCAE) version 4.0 will be utilized for AE reporting. All appropriate treatment areas should have access to a copy of the CTCAE version 4.0. A copy of the CTCAE version 4.0 can be downloaded from the CTEP web site http://ctep.cancer.gov/protocolDevelopment/electronic_applications/ctc.htm.
- **For expedited reporting purposes only:**
 - AEs for the agent that are ***bold and italicized*** in the CAEPR (*i.e.*, those listed in the SPEER column, Section 7.1.1) should be reported through CTEP-AERS only if the grade is above the grade provided in the SPEER.

- Other AEs for the protocol that do not require expedited reporting are outlined in section 7.3.4.
- **Attribution** of the AE:
 - Definite – The AE is *clearly related* to the study treatment.
 - Probable – The AE is *likely related* to the study treatment.
 - Possible – The AE *may be related* to the study treatment.
 - Unlikely – The AE is *doubtfully related* to the study treatment.
 - Unrelated – The AE is *clearly NOT related* to the study treatment.

7.3 Expedited Adverse Event Reporting

7.3.1 Expedited AE reporting for this study must use CTEP-AERS (CTEP Adverse Event Reporting System), accessed via the CTEP Web site (<https://eapps-ctep.nci.nih.gov/ctepaers>). The reporting procedures to be followed are presented in the “NCI Guidelines for Investigators: Adverse Event Reporting Requirements for DCTD (CTEP and CIP) and DCP INDs and IDEs” which can be downloaded from the CTEP Web site (http://ctep.cancer.gov/protocolDevelopment/electronic_applications/adverse_events.htm). These requirements are briefly outlined in the tables below (Section 7.3.3).

In the rare occurrence when Internet connectivity is lost, a 24-hour notification is to be made to CTEP by telephone at [contact]. Once Internet connectivity is restored, the 24-hour notification phoned in must be entered electronically into CTEP-AERS by the original submitter at the site.

7.3.2 CTEP-AERS is programmed for automatic electronic distribution of reports to the following individuals: Study Coordinator of the Lead Organization, Principal Investigator, and the local treating physician. CTEP-AERS provides a copy feature for other e-mail recipients.

The Coordinating Center of the Lead Organization is responsible for submitting to the CTSU documentation of AEs that they deem reportable for posting on the CTSU protocol web page and inclusion on the CTSU bi-monthly broadcast.

7.3.3 Expedited Reporting Guidelines

Use the NCI protocol number and the protocol-specific patient ID assigned during trial registration on all reports.

Note: A death on study requires both routine and expedited reporting regardless of causality, unless as noted below. Attribution to treatment or other cause must be provided.

Death due to progressive disease should be reported as **Grade 5 “Neoplasms benign, malignant and unspecified (incl cysts and polyps) - Other (Progressive Disease)”**

under the system organ class (SOC) of the same name. Evidence that the death was a manifestation of underlying disease (e.g., radiological changes suggesting tumor growth or progression; clinical deterioration associated with a disease process) should be submitted.

Late Phase 2 and Phase 3 Studies: Expedited Reporting Requirements for Adverse Events that Occur on Studies under an IND/IDE within 30 Days of the Last Administration of the Investigational Agent/Intervention^{1,2}

FDA REPORTING REQUIREMENTS FOR SERIOUS ADVERSE EVENTS (21 CFR Part 312)

NOTE: Investigators **MUST** immediately report to the sponsor (NCI) **ANY** Serious Adverse Events, whether or not they are considered related to the investigational agent(s)/intervention (21 CFR 312.64)

An adverse event is considered serious if it results in **ANY** of the following outcomes:

- 1) Death
- 2) A life-threatening adverse event
- 3) An adverse event that results in inpatient hospitalization or prolongation of existing hospitalization for \geq 24 hours
- 4) A persistent or significant incapacity or substantial disruption of the ability to conduct normal life functions
- 5) A congenital anomaly/birth defect.
- 6) Important Medical Events (IME) that may not result in death, be life threatening, or require hospitalization may be considered serious when, based upon medical judgment, they may jeopardize the patient or subject and may require medical or surgical intervention to prevent one of the outcomes listed in this definition. (FDA, 21 CFR 312.32; ICH E2A and ICH E6).

ALL SERIOUS adverse events that meet the above criteria **MUST** be immediately reported to the NCI via AdEERS within the timeframes detailed in the table below.

Hospitalization	Grade 1 Timeframes	Grade 2 Timeframes	Grade 3 Timeframes	Grade 4 & 5 Timeframes
Resulting in Hospitalization \geq 24 hrs		10 Calendar Days		24-Hour 5 Calendar Days
Not resulting in Hospitalization \geq 24 hrs	Not required		10 Calendar Days	

NOTE: Protocol specific exceptions to expedited reporting of serious adverse events are found in the Specific Protocol Exceptions to Expedited Reporting (SPEER) portion of the CAEPR

Expedited AE reporting timelines are defined as:

- o "24-Hour; 5 Calendar Days" - The AE must initially be reported via AdEERS within 24 hours of learning of the AE, followed by a complete expedited report within 5 calendar days of the initial 24-hour report.
- o "10 Calendar Days" - A complete expedited report on the AE must be submitted within 10 calendar days of learning of the AE.

¹Serious adverse events that occur more than 30 days after the last administration of investigational agent/intervention and have an attribution of possible, probable, or definite require reporting as follows:

Expedited 24-hour notification followed by complete report within 5 calendar days for:

- All Grade 4, and Grade 5 AEs

Expedited 10 calendar day reports for:

- Grade 2 adverse events resulting in hospitalization or prolongation of hospitalization
- 1. Grade 3 adverse events

²For studies using PET or SPECT IND agents, the AE reporting period is limited to 10 radioactive half-lives, rounded UP to the nearest whole day, after the agent/intervention was last administered. Footnote "1" above applies after this reporting period.

Effective Date: May 5, 2011

7.3.4 Additional Protocol-Specific Expedited Adverse Event Reporting Exclusions

For this protocol only, the AEs/grades listed below do not require expedited reporting via CTEP-AERS. However, they still must be reported through the routine reporting mechanism (Section 7.4):

CTCAE SOC	Adverse Event	Grade
Blood and lymphatic system disorders	Anemia	Grade 3 or 4
Investigations	White blood cell decreased	Grade 3 or 4
	Lymphocyte count decreased	Grade 3 or 4
	Neutrophil count decreased	Grade 3 or 4
	Platelet count decreased	Grade 3 or 4

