2.2.7 Milled MLN0128 (TAK-228) Drug Substance (DS, process B)

In order to allow more predictable absorption of MLN0128 (TAK-228) after oral administration and to allow scale-up manufacturing of MLN0128 (TAK-228) capsules, Millennium/Takeda developed a new milled formulation of the agent. The physical milling step during the granulation process controls particle size distribution of MLN0128 (TAK-228). In order to observe whether this milling step altered the safety and PK profile of MLN0128 (TAK-228), the company performed *in vivo* studies with PK analysis of milled MLN0128 (TAK-228). These studies indicated that the milled formulation may result in faster absorption with possibly higher maximum concentration (C_{max}), which could result in a different safety profile, compared to the previous unmilled API capsules. In rats, the mean AUC milled/unmilled was 2.97 ± 0.8, while in monkeys, it was 1.68 ± 0.86. The C_{max} ratios were 1.68 ± 0.86.

Takeda developed new MLN0128 (TAK-228) capsules containing milled active pharmaceutical ingredient (API) for clinical studies in 1 mg, 3 mg, and 5 mg strengths. Patients receiving the milled formulation were added onto ongoing studies C31001 and C31002, as well as a new study MLN0128-1004, to determine the PK parameters of milled and unmilled MLN0128 in patients administered single doses under both fasted and fed conditions, with various treatment cohorts including daily and weekly administration of milled MLN0128 (TAK-228).

The recommended dose of milled MLN0128 (TAK-228) was evaluated in 17 patients of

MLN0128-1004, with PK, safety, and tolerability assessed. Six patients were given a 4 mg QD dose of milled MLN0128 (TAK-228) and 3 patients had observed DLT (rash, appetite loss and fatigue). A dose of 3 mg QD was given to 11 patients with only 1 DLT (decreased platelets) observed. The 3 mg QD dose of MLN0128 (TAK-228) was declared the RP2D, and was generally well tolerated and demonstrating objective responses in patients.

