Recommended management: Loperamide antidiarrheal therapy Dosage schedule: 4 mg at first onset, followed by 2 mg with each loose motion until diarrhea-free for 12 hours (maximum dosage: 16 mg/24 hours) Adjunct anti-diarrheal therapy is permitted and should be recorded when used.	

Hyperglycemia	Management/Next Dose for MLN0128 (TAK-228)
≤ Grade 1	No change in dose. Optimize blood sugar control. *
Grade 2	No change in dose. Optimize blood sugar control.
Grade 3 Asymptomatic	No change in dose. Optimize blood sugar control.
Grade 3 Symptomatic or >7 days on therapy	Hold** until < Grade 2. Resume at one dose level lower.
Grade 4	Off protocol therapy
* If medical therapy is needed, metformin is preferred unless contraindicated. Sulfonylurea can be added if metformin does not control blood glucose level. If this fails to bring it to ≤ G1 within 1 month, then oral hypoglycemics can be stopped and insulin used.	
**Patients requiring > two dose reductions should go off protocol therapy.	
Hyperglycemia will be based on fasting glucose level.	

Thrombocytopenia and neutropenia	Management/Next Dose for MLN0128 (TAK-228)
≤ Grade 1	No change in dose
Grade 2	Hold until ≤ Grade 1. Resume at same dose level.
Grade 3	Hold* until ≤ Grade 1. Resume at one dose level lower
Grade 4	Off protocol therapy
This dose modification for thrombocytopenia and neutropenia only pertains to	

Thrombocytopenia and neutropenia	Management/Next Dose for MLN0128 (TAK-228)
	patients in remission. Thrombocytopenia and neutropenia will not be considered dose limiting during remission induction.
	*Patients requiring a delay of >4 weeks if related to MLN0128 (TAK-228) should go off protocol therapy. This only will be counted if patients are in remission (CR).
	**Patients requiring > two dose reductions should go off protocol therapy.

Non-hematological toxicity:

Non-hematological toxicities of fatigue, electrolyte abnormalities and abnormal liver function tests, including bilirubin, transaminases and alkaline phosphatase will only require dose modification if they are likely or definitely related to MLN0128 (TAK-228) and persist more than 7 days. Neutropenic fever and infectious toxicities are only counted for if patients achieve remission and then develop these adverse events.

Non-Hematological Toxicity

Event	Management/Next Dose for MLN0128 (TAK-228)
≤ Grade 1	No change in dose
Grade 2	Hold until ≤ Grade 1. Resume at same dose level.

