13.4.5 Adverse Events

All eligible patients that have initiated treatment will be considered evaluable for assessing adverse event rate(s). The maximum grade for each type of adverse event will be recorded for each patient, and frequency tables will be reviewed to determine patterns. Additionally, the relationship of the adverse event(s) to the study treatment will be taken into consideration.

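### The adverse-event table uses each patient's worst grade without reference to baseline, so it can mix leukemic with drug-related cytopenia; separately, the 7.3.4 reporting exemption needs reconciling with Section 6 and the SPEER.

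*Combined protocol and SAP*

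**What the plan says.** **Tabulation.** Section 13.4.5 provides that "The maximum grade for each type of adverse event will be recorded for each patient, and frequency tables will be reviewed to determine patterns". It adds that relationship to treatment will be considered, without a method. Section 13.7.1 makes patients evaluable for toxicity from their first dose and says nothing about abnormalities already present.

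**Entry.** Section 3.1.2 requires at least 10% marrow blasts. The laboratory limits in 3.1.7 cover bilirubin, transaminases, creatinine, glucose and HbA1c. Section 3.2.2 sets an upper limit on the white cell count. No minimum is set for hemoglobin, neutrophils or platelets.

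**Expedited reporting.** Section 7.3.4 says: "For this protocol only, the AEs/grades listed below do not require expedited reporting via CTEP-AERS". The list is anemia and decreased white cell, lymphocyte, neutrophil and platelet counts, each at grade 3 or 4. It has no condition on baseline, attribution, cycle or remission, and it keeps routine reporting. Section 7.2 presents this list as an addition to the SPEER: "Other AEs for the protocol that do not require expedited reporting are outlined in section 7.3.4". The SPEER column in 7.1.1 exempts anemia and platelets only up to grade 2.

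**Dose modification.** For platelets and neutrophils, Section 6 separates two settings. "Thrombocytopenia and neutropenia will not be considered dose limiting during remission induction", whereas in remission grade 3 leads to a hold and a lower dose level, and grade 4 to the end of protocol therapy.

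**The concern.** In leukemia, low counts may come from the disease, the drug or both. A worst-grade table does not distinguish a patient who entered at grade 4 and stayed there from one who entered at grade 1 and fell to grade 4 on treatment. The question matters for this agent: Section 2.2.7 reports of the milled formulation that "A dose of 3 mg QD was given to 11 patients with only 1 DLT (decreased platelets) observed", and 3 mg daily is this trial's starting dose (given on days 1-21 of each cycle). A single-arm trial has no control group to supply the background rate, so each patient's own baseline is the only measured reference.

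The reporting question is related but separate. Section 6 regards a low platelet or neutrophil count in remission as different in kind from one during induction. Section 7.3.4 draws no such line, so a grade 4 count that ends a responder's protocol therapy needs no expedited report under that section.

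**Working it through.** The plan gives no figure on this point to reproduce. The check is a comparison of sections, followed by an illustration of size.

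**Step 1: is baseline grade used anywhere?** The text available in 3.1, 3.2, 7.2, 7.4, 13.4.5 and 13.7.1 contains no rule limiting the table to worsening from baseline. Most rows of the Section 10 calendar are missing from the text reviewed, so a rule placed there could not be checked.

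**Step 2: how far could the table be distorted?** Let *b* be the share entering with a grade 3-4 cytopenia and *d* the share of the remainder who newly reach grade 3-4 on treatment. If baseline abnormalities are recorded as events, a worst-grade table shows

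shown = *b* + (1 − *b*) × *d*.

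With N = 26 evaluable patients (Section 13.2.1), and with *b* and *d* both assumed:

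| *b* | *d* | Shown | Patients of 26 | Newly grade 3-4 |
|---|---|---|---|---|
| 20% | 0% | 20% | 5.2 | 0 |
| 20% | 30% | 44% | 11.4 | 6.2 |
| 60% | 0% | 60% | 15.6 | 0 |
| 60% | 10% | 64% | 16.6 | 1.0 |
| 80% | 0% | 80% | 20.8 | 0 |
| 80% | 30% | 86% | 22.4 | 1.6 |

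For example, 0.60 + 0.40 × 0.10 = 0.64, and 26 × 0.64 = 16.6, of which 26 × 0.40 × 0.10 = 1.0 is new. At *b* = 80%, moving from no drug effect to 30% of those at risk raises the table only from 20.8 to 22.4 patients. The higher the baseline share, the less the table responds to the drug.

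**Step 3: the expedited-reporting provisions side by side.**

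| Term at grade 3-4 | SPEER (7.1.1) | 7.3.4 | Section 6 cytopenia table |
|---|---|---|---|
| Anemia | Exempt only to grade 2 | Exempt at all times | Not covered |
| Platelets | Exempt only to grade 2 | Exempt at all times | Remission only |
| Neutrophils | Not listed | Exempt at all times | Remission only |
| White cells, lymphocytes | Not listed | Exempt at all times | Not covered |

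Section 7.3.4 therefore removes reports that the SPEER would keep for two terms, and for two terms it does not follow the split made in Section 6. The overlap is platelets.

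**Step 4: how many patients does the remission question concern?** At the design's true CR/CRi rates of 10% to 30%, a full cohort gives 26 × 0.10 = 2.6 to 26 × 0.30 = 7.8, or about 3 to 8 patients. If 10% to 30% of them (assumed) had a new grade 3-4 cytopenia, that is 3 × 0.10 = 0.3 to 8 × 0.30 = 2.4 patients. These are patients, not reports; one patient could generate several reports.

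**The case against.** The strongest reply is that nothing in the plan says a cytopenia present before the first dose is entered as an adverse event. Toxicity evaluation starts at first dose, every event carries a five-level attribution (7.2), and baseline handling may sit in the case report forms or the NCI guidelines that the protocol cites. This stands against a reading that a reader might infer, namely that the table counts leukemia as toxicity. The documents leave that risk open; they do not prescribe it. It does not close the gap, because 13.4.5 is where the analysis rule belongs and it has none. Attribution is a judgment; a baseline grade is a measurement.

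A reader might also infer that most patients will enter at grade 3-4, since Section 9.1.1.5 calls a platelet count of 10,000 adequate. That remark concerns bleeding risk at blood sampling and says nothing about counts at entry. The documents show only that severe cytopenia at entry is permitted.

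A third tempting reading is that drug-caused cytopenias in responders go unseen. They do not. Section 7.3.4 keeps them in routine reporting, with data submitted at least every two weeks (12.2.2). The principal investigator and statistician have access at all times (12.1), and the monitoring board reviews safety data at least twice a year (13.6). Section 13.6.1 lets the team suspend accrual for unexpected profiles that have not crossed its rule. Grade 5 events and unlisted terms, such as infection and bleeding, are not exempted by 7.3.4. Nor are all five terms established drug effects: 7.1.1 places "Lymphocyte count decreased; Neutrophil count decreased; White blood cell decreased" among events with insufficient evidence of causation. And CRi by definition allows residual neutropenia or thrombocytopenia (11.1.2), so a low count in remission need not be new.

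Finally, which known hematologic events to expedite in a leukemia trial is largely the sponsor's policy choice. That is fair, and it is why the request on 7.3.4 is to reconcile and state the intent.

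**Conclusion.** The tabulation point holds and should be acted on. As written, 13.4.5 can produce a cytopenia table that mixes disease and drug, by an amount set mainly by the unknown baseline share. The 5 to 21 of 26 patients is an illustration resting on an assumed share of 20% to 80%, no drug effect, and baseline grades being recorded as events; it is not an estimate for this trial.

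The reporting point is a request for clarification. The 7.3.4 exemption is unconditional, departs from the SPEER for anemia and platelets, and does not follow the Section 6 distinction for platelets and neutrophils.

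No decision rule changes. The only hematologic DLT in 13.5.2 is marrow hypoplasia lasting more than 50 days, the 13.6.1 triggers count grade 4 non-hematologic events only, and the efficacy rule uses CR/CRi. What is affected is how well the trial can describe the drug's hematologic toxicity.

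**What to change.** **Section 13.4.5.** For anemia and the white cell, lymphocyte, neutrophil and platelet terms, add shift tables of baseline grade against worst grade on treatment, and count only worsening from baseline. Define baseline as the last count before the first dose. Show the tables by attribution, and separately before and after first remission (first CR or CRi). After remission, take the grade at remission as the reference, because CRi allows residual cytopenia. Give the number at risk of worsening beside each count, since a patient already at grade 4 has almost no room to worsen on a count scale.

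**Section 7.3.4.** Reconcile with Section 6 and the SPEER, and state whether the exemption is meant to apply in remission. If so, give the reason. The text should say how it treats the three terms that Section 6 does not cover, and whether CRi counts as remission. It should also say how the exemption relates to 7.3.3, which points only to the SPEER for exceptions for serious events.

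**Cost.** A little extra analysis. White cells are needed for eligibility, and neutrophils and platelets for response. Hemoglobin and lymphocytes are assumed to come from the same blood counts, as the calendar rows could not be read. The 7.3.4 change is a sentence or two of text.
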